8.3 Other study parameters

MRI: the level of disc herniation on MRI will be compared to the clinical diagnosis (made before MRI) and the percentage of clinical diagnosis prediction success can be calculated.

The size and shape of disc herniation, disc degeneration (Pfirrmann scale), vertebral end plate changes, and facet degeneration (Weishaupt scale) will be correlated to baseline clinical data using t-tests.

Histology: the number of M1 and M2 macrophages will be correlated to NRS leg pain and ODI at all time points using t-tests and mixed models analysis.

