2. OBJECTIVES

Primary study objective:

To study effectivity of the epidural injection with analgesic and anti-inflammatory medication to relieve the symptoms within two weeks follow up.

It will be evaluated what the average leg pain score is in both treatment arms at two weeks follow up. It will be evaluated how long the effect lasts.

The leg pain and functionality at 4 weeks after randomization will also be evaluated to get informed on the responsiveness on TEI in a somewhat later stage.

Secondary study objectives:

To evaluate the outcome of TEI in the first two weeks after randomization as a predictor of NRS leg pain at 14-16 and ca 26 weeks after onset of leg pain.

Ideally, responsiveness to TEI can predict the clinical condition at 14-16 weeks after onset of sciatica. The hypothesis is that being non-responsive to TEI within two weeks, predicts an unsatisfactory condition after 14-16 weeks of suffering. This is the category of patients that in contemporary care in the Netherlands will be offered a surgical intervention. If our hypothesis is correct, in the future, this population of patients can be offered a surgical intervention at an earlier time point.

The ca 26-week time point is chosen since in the Sciatica trial [2], both the conservative and the surgical group demonstrated comparable outcome data.

Patients in this study are included while suffering from severe leg pain for 3-8 weeks.

Presumably most patients will enter the study with 4-6 weeks of leg pain. This means that on average 10 weeks after randomization, the 14-16 week leg pain time point is reached. This means that 21 weeks after randomization the ca 26-week leg pain time point is reached.

The response in NRS leg pain, ODI and patient satisfaction at 1 week after injection and at 2 weeks after injection will be correlated to the value of these parameters at 10 and 21 weeks after randomisation.

To evaluate the cost-effectivity of analgesic/anti-inflammatory epidural injections to relieve symptoms of early sciatica.

A substantial portion of the patients in this study will eventually have an MRI of the lumbar spine. These MRIs will be evaluated according to our standard MRI evaluation protocol, that has been proven to generate additional successful conclusions and subsequent publications in the past [10-15]. Protruding disc, disc and vertebral end plate changes (MODIC) will be correlated to clinical data.

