NRS leg pain that decreases below the value of 4 (on a 10 point scale) within two weeks after TEI is documented as successful effect of TEI. NRS leg pain that remains higher than a value of 4 at a time interval of two weeks after TEI makes a patient eligible for surgery if the patient requests for surgery. If surgery is requested by the patient (either in the control or intervention group), general guidelines for timing of surgery will be conducted, meaning that the patient is encouraged to postpone surgery till 14-16 weeks after onset of pain. This decision is made using Shared Decision Making and it is possible that the patient is operated before the 14-16 week time point. The patients who are randomized cannot be operated in the first two weeks after randomization, unless sudden loss of strength or a cauda equina syndrome is reported. We expect that during these two weeks TEI will have its effect. Four

weeks after randomization the outcome parameters are measured again to be informed on the late effect of TEI. Patients will be followed up for a total duration of 21 weeks starting from the moment of randomization. Questionnaires will be filled in at baseline, 1, 2, 4, 10 and 21 weeks follow-up. A schematic overview of the study procedures is outlined in figure 1. Note that this figure does not hold into account that it is possible for patients randomized to the treatment group to receive additional injections if necessary.

[figure not shown]

Fig.1 Flow diagram of study procedures

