4.2 Inclusion criteria

In order to be eligible to participate in this study, a subject must meet all of the following criteria:

- Sciatica;
- Leg pain of 6 or more on a 10 point NRS (Numeric Rating Scale) scale with a duration of >3 and <8 weeks;
- Patient is willing to accept the possible costs for the treatment by the pain physician
- Informed consent.

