6.1.3 Other study parameters

Data with respect to the following variables will be collected at baseline:

- Demographic data;
- Age, gender, length, weight, BMI, tobacco exposure, alcohol abuse;
- History of previous radicular symptoms in the legs;
- Usage of pain medication.

Data with respect to the following items will be collected concerning TEI:

- Timing of administration (days after randomization);
- Number of injections and timing of those;
- NRS leg pain after injection;
- Other complications.

Data during follow up will be collected:

- If an MRI is performed: MRI data;
- If surgery is performed: disc material for histology.

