6.3 Study procedures

Patients that are diagnosed by the GP with acute sciatica (3-8 weeks after onset of pain, NRS \geq 6) that meet in- and exclusion criteria will be offered the study. If patients are willing to be randomized, they will be contacted by the study investigator. The study investigator will inform the patients again and checks whether patients have access to e-mail. This is done to make sure that they can fill in the questionnaires online (a web-based database with questionnaires is used for data collection (Castor, LUMC)). The study investigator will ask for informed consent. Randomization will take place. If patients are randomized to the intervention group, they will be sent to the anaesthesiologist and planned for TEI within 4 days after randomization without visiting the neurologist. If patients are randomized to the

control group, they will receive oral pain medication according to the care of the general practitioner.

The patient will be invited to the hospital where baseline data will be gathered and questionnaires will be filled in. During this contact the study investigator will guide the patient through the online questionnaire fill-in procedure to get the patient accustomed with this procedure.

Questionnaires will be filled in after 1, 2, 4, 10 and 21 weeks after randomization for both the control group and TEI group.

If leg pain remains severe after the 2 weeks after randomization primary endpoint, patients can be referred to the neurologist if the general practitioner deems it necessary. Patients can be offered surgery if applicable.

If an MRI is made during the process, MRI data will be gathered as mentioned above.

If a lumbar discectomy is performed, disc tissue will be gathered during surgery and analysed as mentioned above.

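### Section 8.3 relates MRI features to baseline scores only, although scans are unscheduled follow-up events; for herniation size and shape, scores nearer the scan should be added

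*Combined protocol and SAP*

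**What the plan says.** The MRI analysis appears in Section 8.3, Other study parameters. Herniation level is compared with the clinical diagnosis; that part is not at issue. The remaining features (herniation size and shape, Pfirrmann grade, end plate changes and facet grade) are tied to one time point: "facet degeneration (Weishaupt scale) will be correlated to baseline clinical data using t-tests".

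The scan itself has no scheduled date:

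- Section 2: "A substantial portion of the patients in this study will eventually have an MRI of the lumbar spine".
- Section 6.1.3, under data collected during follow-up: "If an MRI is performed: MRI data".
- Section 6.3: "If an MRI is made during the process, MRI data will be gathered as mentioned above".

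Section 6.3 sends patients in the injection arm to the anaesthesiologist within 4 days of randomisation without a neurologist visit. It describes specialist referral later: "If leg pain remains severe after the 2 weeks after randomization primary endpoint, patients can be referred to the neurologist". Section 3 sets the end of observation: "Patients will be followed up for a total duration of 21 weeks starting from the moment of randomization".

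NRS leg pain, NRS back pain and ODI are measured at baseline and at weeks 1, 2, 4, 10 and 21 (Sections 6.1.1 and 6.1.2). Entry requires "Leg pain of 6 or more on a 10 point NRS (Numeric Rating Scale) scale" (Section 4.2).

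**The concern.** The plan pairs a scan of unknown date with scores taken around randomisation. If most scans follow referral for persisting pain, they come weeks or months after those scores and, in one arm, after the injection. Herniation size and shape may have changed by then, so the image need not show the disc that went with the baseline pain. A null association could then mean that there is no relation, or that the two measurements describe different moments. The plan has no way to separate these.

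A second, smaller issue concerns one score. Baseline NRS leg pain lies mostly in the upper part of its scale because of the entry criterion. Less spread in that score means less precision for any association with it.

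What is at stake is the usefulness of an exploratory analysis. The treatment comparison is not involved.

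**Working it through.** **No planned figure to reproduce.** The documents give no sample size, effect size or number of scans for the MRI analysis. The only planned size is for the primary endpoint in Section 4.4, and it reproduces: 2 × (1.960 + 1.282)² × 2.6² / 1.5² = 63.1, rounded up to 64 per group; 128 / 0.9 = 142.2, against a stated 142. Nothing here changes it.

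**Step 1: when scans can occur.** Sections 2, 6.1.3 and 6.3 make the scan conditional and place it in follow-up. Routine neurologist referral is described after the 2-week endpoint, and follow-up ends at week 21. The inferred gap from baseline to scan is therefore about 2 to 21 weeks. This is an inference: no section gives scan dates or rules out an earlier scan.

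**Step 2: how close a collected score is.** Visits fall at weeks 1, 2, 4, 10 and 21. The largest gap between visits is 21 − 10 = 11 weeks, so without further conditions the nearest visit is at most 11 / 2 = 5.5 weeks away. If the visit must also precede surgery, that limit no longer holds. Illustrative cases:

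| Scan | Weeks from baseline | Nearest usable visit | Weeks from that visit |
|---|---|---|---|
| Week 3 | 3 | Week 2 or 4 | 1 |
| Week 7 | 7 | Week 4 or 10 | 3 |
| Week 15.5 | 15.5 | Week 10 or 21 | 5.5 |
| Week 20, surgery before week 21 | 20 | Week 10 | 10 |

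In each case a nearer score exists than baseline, but the distance varies.

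**Step 3: what the same section does for histology.** The other analysis in Section 8.3 relates macrophage counts to NRS leg pain and ODI at every time point, with mixed models as well as t-tests. The method needed for MRI is already in the plan. Section 2 speaks of clinical data without naming a time point, so the limit to baseline comes from Section 8.3 alone.

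**Step 4: the leg pain range.** A score confined to 6–10 has an SD of at most (10 − 6) / 2 = 2.0, and of 1.41 if spread evenly over the five values. Section 4.4 uses 2.6, but as a week-2 planning value, not for unselected patients. Going further needs assumptions. Take an unselected 0–10 score as approximately normal and rounded to whole points, with mean 4 to 7 and SD 2.0 to 2.6. Keeping scores of 6 or more leaves a ratio u of restricted to full SD of 0.47 to 0.70. The range-restriction formula is r′ = r·u / √(1 − r² + r²·u²). For an assumed r = 0.30:

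- u = 0.47: 0.141 / √(0.91 + 0.020) = 0.15
- u = 0.70: 0.210 / √(0.91 + 0.044) = 0.21

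The number of scanned patients for 80% power at two-sided 5% is ((1.960 + 0.842) / atanh r)² + 3. This gives 85 for r = 0.30, 176 for 0.21 and 347 for 0.15, against 142 patients in the whole trial. The value r = 0.30 is an illustration with no source in the documents, and the formula is for a Pearson correlation, so it maps only loosely onto the planned t-tests.

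**The case against.** The strongest reply is that baseline is a sound anchor. It is common to all patients and, for nearly all, comes before treatment. A score near the scan is shaped by the pain that prompted the scan and, in one arm, follows the injection. This stands, and it is the reason to keep the baseline comparison and add to it.

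It can also be said that severe sciatica is the target population, so the association within that range is the relevant one. This stands too: within the trial population, less spread costs precision and does not bias the estimate.

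A reader might infer several stronger claims that the documents do not support:

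- *All baseline scores are truncated.* Only NRS leg pain has an entry threshold. ODI, NRS back pain and EQ-5D have none.
- *Every recorded baseline leg pain score is 6 or more.* The GP applies the threshold at diagnosis, at least 48 hours for consideration follow (Section 4.1), and Section 6.3 describes the baseline questionnaires after randomisation. Some recorded scores may be lower.
- *Later scores would cover a wider range.* This is unproven in patients scanned largely for persisting pain.
- *A sizeable true correlation would be hidden.* No section supplies one, and the Introduction reports that pain score does not correlate with herniation size.
- *All MRI features are equally affected by timing.* The argument is made for herniation size and shape; the documents give no reason to expect material change in the degeneration grades over these weeks.
- *Sections 2 and 8.3 contradict each other.* The first is general and the second specific.

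**Conclusion.** The concern holds in limited form. Section 8.3 uses baseline scores alone for scans that are unscheduled and probably mostly made after week 2. For herniation size and shape this leaves a null result hard to interpret; for disc, end plate and facet degeneration the case is weaker. The inferred delay of about 2 to 21 weeks rests on the referral pathway and the length of follow-up, not on stated scan dates.

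The restricted range of baseline NRS leg pain is a separate loss of precision for that one score. Its size depends on an unselected distribution and a true correlation that the documents do not give, so the figures above are illustrations, not estimates.

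This is a low-cost improvement to an exploratory analysis. The primary result and its sample size are unaffected.

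**What to change.** In Section 8.3:

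1. Record the MRI date, taken from the hospital record that Section 10.1 already uses for MRI data.
2. Keep the baseline comparison. Beside it, relate MRI findings, herniation size and shape in particular, to NRS leg pain, NRS back pain and ODI at the pre-surgery visit nearest the scan, or at all pre-surgery time points by mixed model as planned for histology.
3. Adjust for arm and for time from randomisation to scan.
4. Exclude scans made after discectomy.
5. State that the results are exploratory and apply to the subset scanned in usual care, probably mostly for persisting pain.

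The cost is a few lines of analysis text and one extra extracted date; no scan, visit or reader is added. There are two drawbacks. The interval from visit to scan will vary, reaching about 10 weeks when a late scan is followed by surgery before week 21. Scores near the scan are themselves selected for persisting pain.

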A portion of the patients in this study will eventually be operated. Disc material from these patients will be evaluated for the presence (and type) of macrophages and these data will be correlated to MRI and clinical data. These additional outcome measures can be combined with the research lines on etiology of sciatica that are executed in the Neurosurgery Department of the LUMC [16].

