3. STUDY DESIGN

This is a prospective, open-label, randomized controlled trial on patients suffering from acute sciatica (3-8 weeks pain in the leg with a NRS ≥ 6) (see inclusion and exclusion criteria) in which consecutive patients who meet the inclusion criteria are invited to participate in the trial. The trial will take place at the Spaarne Gasthuis Hospital (SG) in Hoofddorp and Haarlem, the Netherlands in cooperation with researchers from Leiden University Medical Center (LUMC), Leiden, the Netherlands. Patient recruitment will occur at GP practices (GP collective Haarlemmermeer and Kennemerland, 185 GP's). The GP will diagnose the patient and, if the patient is diagnosed with sciatica, refer to the study investigator.

Eligible patients that are willing to participate are randomized to treatment with transforaminal epidural injections (treatment group) or standard conservative care (control group).

Randomization will take place using block randomization in a 1:1 allocation ratio. Patients from the treatment group will be treated with TEI, oral pain medication and, if deemed necessary by the GP, physiotherapy. The control group will only receive oral pain medication and if deemed necessary additional physiotherapy. For this study, the control group will not include placebo injections since we want to compare treatment with injections to treatment without injections. The focus will not be on the type of medication that is contained in the injection. Furthermore, a control group without injections will demonstrate what percentage of patients will experience spontaneous relief of symptoms (only using medication and/or physiotherapy) as it is known that in a significant part of the patients sciatica resolves without any intervention.

At baseline, clinical and demographic data are gathered for patients in both groups. Patients from the treatment group will receive TEI within 4 days after randomization. Patients from this group can receive multiple injections but an injection is only repeated after a certain interval time according to usual anaesthesiological guidelines. For all injections, details on timing, frequency and prevailing complications will be gathered.

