Costs (Cost intervention, health care use, and loss of productivity): Cost diaries will be filled out at 10 and 21 weeks after randomisation. Health care utilization (including physiotherapy, visits to GP and specialists, nursing care and medication), patient costs, and absenteeism will be measured using cost diaries filled out by the patient.

Complications: Post-TEI exacerbation of NRS leg pain (>1 point additional leg pain) that lasts for at least 24 hours will be documented as a clinically relevant complication of TEI. Other rare adverse events from treatment with TEI such as pain at site of injection, persisting numbness, vasovagal reaction, accidental discal puncture, accidental dural puncture or headache will be recorded as well.

Radiological parameters: the level of disc herniation, the size and shape of disc herniation, disc degeneration (Pfirrmann scale), vertebral end plate changes, and facet degeneration (Weishaupt scale) will be evaluated by two independent researchers, blinded to clinical and histological data, on T2 weighted sagittal and transversal MRI.

Histology: During surgery, the herniated disc material will be collected and fixed in 4% formaldehyde solution. For evaluation, the tissue will be subsequently embedded in paraffin blocks. These blocks will be stained with Hematoxylin and used for general macrophage staining (CD68), and subtype macrophage staining: M1(iNOS & CD40) and M2 (Arg1 & CD163), T cell staining (CD45-RO) and B cell staining (CD20). Furthermore, presence of Propionibacterium Acnes and Staphylococcus Epidermidis will be verified by PCR analysis for 16S rDNA. Positive samples will be gram stained for further identification of the bacteria.

All histological data will be quantified by two independent researchers, blinded to clinical and MRI data, and an inter-agreement analysis will be conducted.

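### Section 8.3 relates macrophage counts from surgical disc tissue to pain and disability at every visit, without separating scores before and after surgery and without a term for TEI received

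*Combined protocol and SAP*

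**What the plan says.** The histology analysis is one sentence in section 8.3: "the number of M1 and M2 macrophages will be correlated to NRS leg pain and ODI at all time points", by t-tests and mixed models. It names no covariate, no injection or arm term, no before/after-surgery indicator and no subset of visits. Section 2 adds only that "these data will be correlated to MRI and clinical data".

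The design facts that bear on this sentence are in other sections:

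- Tissue (section 6.1.2): "During surgery, the herniated disc material will be collected and fixed in 4% formaldehyde solution". The analysis set is therefore operated patients, each with one specimen.
- Injection (section 3): "Patients from the treatment group will receive TEI within 4 days after randomization", and repeat injections are possible. For the other arm, "The control group will only receive oral pain medication and if deemed necessary additional physiotherapy".
- Earliest surgery (section 3): "The patients who are randomized cannot be operated in the first two weeks after randomization", apart from two neurological emergencies. Patients are then encouraged to wait until 14-16 weeks after onset, but earlier surgery is possible.
- Scores (sections 3 and 6.1): baseline and weeks 1, 2, 4, 10 and 21 after randomisation.
- Data on exposure: section 6.1.3 collects "Number of injections and timing of those", and section 10.1 has TEI and surgery data taken from the hospital record.

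**The concern.** Two features of the design meet in that sentence.

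First, the sampled tissue is present for some scores and gone for others. A pre-operative score describes pain while the herniation was in place; a post-operative score describes recovery after discectomy. These are different questions, one of association and one of prognosis. Section 1 gives unexplained differences in pain between patients as the reason for collecting the discs, which is the first question.

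Second, specimens from injected patients will almost always be taken after the injection, while control specimens are planned to be unexposed. The protocol calls the injection anti-inflammatory, expects it to lower leg pain (section 4.4), and says that inflammation at the herniation recruits macrophages (section 1). On those premises TEI may be a common cause of the count and of the scores made after injection.

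At stake is the reading of the histology result: a real link could be weakened, or a weak one produced, by the timing of surgery or by treatment.

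**Working it through.** **The plan's own figures.** Section 8.3 gives no sample size, effect size or power for histology, so there is no histology figure to reproduce. The primary sample size supplies some inputs and does reproduce: 2 × (1.96 + 1.2816)² × (2.6/1.5)² = 63.1, so 64 per group and 128 in all; 128/0.9 = 142.2, against 142 stated. It has no other bearing here.

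**1. Which scores fall after surgery.** Section 2 puts 14-16 weeks after onset at about week 10 on average. Over the whole entry window of 3 to 8 weeks, the range is 14 − 8 = 6 to 16 − 3 = 13 weeks after randomisation. Week 10 lies inside that range, and week 21 lies beyond it. Of the six scheduled scores:

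| Surgery | Before | After |
|---|---|---|
| just before week 4 | 3 | 3 |
| week 6 | 4 | 2 |
| about week 10, after that score | 5 | 1 |

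**2. Effect of mixing.** Suppose the count correlates 0.40 with pain before surgery and 0 after it, and the timing of surgery is unrelated to the count (assumptions). With a share q of scores post-operative, a mean drop D at surgery and SD 2.6 (section 4.4):

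r = (1 − q) × 0.40 × 2.6 / √(2.6² + q(1 − q)D²)

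| q | D = 0 | D = 3 (assumed) |
|---|---|---|
| 0.25 | 0.30 | 0.27 |
| 0.50 | 0.20 | 0.17 |
| 0.75 | 0.10 | 0.09 |

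If instead the timing of surgery is related to the count, mixing can create a link. With half the patients operated on by the visit, a 3-point drop, and a count difference of 0.25 to 1 SD between those operated on earlier and later, the induced r is 0.06 to 0.22.

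**3. Effect of TEI as a common cause.** Let p be the share of operated patients who had TEI, dP the TEI effect on pain in SD units, and dM its effect on the count in SD units. With no link within exposure groups:

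r = p(1 − p)·dM·dP / √[(1 + p(1 − p)dM²)(1 + p(1 − p)dP²)]

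Here dP = 1.5/2.6 = 0.577 (section 4.4). The documents give no value for dM, so 0.25, 0.5 and 1.0 are assumed, with p = 0.5. The results are r = 0.034, 0.067 and 0.124. With p = 0.33 they are 0.031, 0.060 and 0.111.

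The number of operated patients is also not given. The only surgery rate in the documents is 40%, from the conservative arm of an earlier trial (section 1). Taking 10% to 40% of 142 as an assumed range gives about 14 to 57. By Fisher's z, with p = 0.5, the nominal 5% error becomes:

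| Operated | dM 0.25 | dM 0.5 | dM 1.0 |
|---|---|---|---|
| 14 | 5.1% | 5.6% | 7.0% |
| 57 | 5.7% | 7.8% | 15.0% |

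Simulation with 57 patients (5,000 runs) gave 8.0% and 14.7% for dM = 0.5 and 1.0 without a TEI term, and 5.2% and 5.5% with one.

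**The case against.** The strongest reply is that the sentence in 8.3 is open rather than wrong. It does not say that visits or arms are pooled; it can be read as a separate test at each visit, plus a mixed model that carries time and might carry treatment. Baseline and weeks 1, 2 and 4 are then mostly pre-operative, and relating counts to later outcome is a legitimate aim, since section 2 speaks of clinical data in general. Much of this stands. But separate tests by visit do not help at week 10, where operated and not-yet-operated patients sit side by side, and they leave week 21 as a measure of recovery reported next to measures of current pain.

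Four further points also stand and limit the claim.

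- A reader might infer that the biomarker result is confounded by TEI. The documents do not support that: they give no effect of TEI on macrophages, and the working applies the full 1.5-point pain effect to operated patients. Under section 3 it is persisting leg pain after TEI that opens the way to surgery, so among operated patients the difference may be smaller or reversed.
- Baseline pain precedes the injection and cannot be changed by it. There the concern is that only operated patients are analysed.
- A reader might also infer that a plain surgery covariate is missing. Every patient with tissue was operated on, so an ever/never term could not be estimated; what matters is whether a score falls before or after the operation.
- Absence of TEI in controls is planned, not certain. Section 4.1 leaves their care to the GP, and section 6.5 foresees refusals in the TEI arm, so allocated arm is an imperfect stand-in for exposure.

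**Conclusion.** The concern holds in a limited form. Followed as written, 8.3 brings in scores from both sides of tissue removal: week 10 mixed, week 21 mostly post-operative. This needs no assumption about TEI, only surgery near the timing the protocol encourages. The loss could be substantial (0.40 down to 0.30, 0.20 or 0.10 as the post-operative share rises from 25% to 75%), but the 0.40, its disappearance after surgery and the 3-point drop are assumptions.

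The missing TEI term is a secondary weakness that affects post-baseline scores only. Its size is unknown and probably modest: r of about 0.03 to 0.12 under the assumed shifts.

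It would go too far to say that the histology aim cannot be met, or that the trial's main result is touched. Early visits remain informative, the analysis sits under other study parameters with no stated power, and the primary comparison at two weeks does not use it.

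**What to change.** Reword the histology paragraph of section 8.3 as follows:

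- Keep NRS leg pain and ODI as the repeated outcome, with the macrophage count as a patient-level predictor. The count is measured once per patient.
- Base the main association analysis on scores up to the last one before each patient's surgery date. Report post-operative scores as a separate prognostic analysis. An acceptable alternative is one model with a time-varying before/after-surgery indicator and its interaction with the count.
- Add one yes/no term for TEI actually received before surgery, applied to post-baseline scores.
- Show counts by TEI exposure and by allocated arm. Describe the number of injections and the days from last injection to surgery among injected patients only, since the interval is undefined for the others and a small subset will not carry several overlapping terms.
- Label the analysis exploratory, and state that it describes operated patients.

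The cost is wording and one or two degrees of freedom in a small subset. Injection data (section 6.1.3) and surgery data (section 10.1) are already to be collected, and no trial procedure changes.
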